#### **4.2.2. Adherence to GS-5829**

##### **4.2.2.1. On-Treatment Adherence**

The level of on-treatment adherence to GS-5829 will be determined by the total amount of GS-5829 administered relative to the total amount of GS-5829 expected to be administered during a subject's actual on-treatment period. Investigator-prescribed interruption, reductions and escalations as specified in the protocol will be taken into account.

The total amount of GS-5829 in mg administered to a subject will be determined by the data collected on the drug accountability CRF using the following formula:

Total amount of Doses Administered (mg) =

$(\Sigma \text{Amount. of Doses Dispensed in mg}) - (\Sigma \text{Amount. of Doses Returned in mg})$

The level of on-treatment adherence will be expressed as a percentage using the following formula:

$$\text{On-Treatment Adherence (\%)} = \left( \frac{\text{Total Amount of Study Drug Administered}}{\text{Study Drug Expected to be Administered on Treatment}} \right) \times 100$$

Descriptive statistics for the level of on-treatment adherence with the number and percentage of subjects belonging to adherence categories ( $< 75\%$ ,  $\geq 75\%$ ) will be provided by dose cohort within each treatment group for the Safety Analysis Set.

#### 4.2.2.2. Average Daily Dose

The average daily dose in mg of GS-5829 administered will be summarized using descriptive statistics.

The average daily dose in mg will be calculated using the following formula:

$$\text{Average Daily Dose (mg)} = \frac{\sum (\text{Daily Dose in mg})}{\text{Total Number of Days on Study Drug}},$$

where Total Number of Days on Study Drug = Last Dosing Date – First Dosing Date + 1.

By-subject listings of study drug administration and drug accountability will be provided by subject ID number in ascending order and visit in chronological order as appropriate.

#### 4.3. Protocol Deviations

Subjects who did not meet the eligibility criteria for study entry, but were enrolled in the study will be summarized regardless of whether they were exempted by the sponsor or not. The summary will present the number and percentage of subjects who did not meet at least 1 eligibility criterion and the number of subjects who did not meet specific criteria by treatment group based on the All Enrolled Analysis Set. A by-subject listing will be provided for those subjects who did not meet at least 1 eligibility (inclusion or exclusion) criterion.

Protocol deviations occurring after subjects entered the study are documented during routine monitoring. The number and percentage of subjects with important protocol deviations by deviation reason (eg, nonadherence to study drug, violation of select inclusion/exclusion criteria) will be summarized by dose cohort within each treatment group and total for the All Enrolled Analysis Set. A by-subject listing will be provided for those subjects with any important protocol deviation.

## 5. BASELINE CHARACTERISTICS

### 5.1. Demographics

Subject demographic variables (ie, age, sex at birth, race, and ethnicity) will be summarized by dose cohort within each treatment group and overall using descriptive statistics for age, and using number and percentage of subjects for sex, race, and ethnicity. The summary of demographic data will be provided for the Safety Analysis Set.

A by-subject demographic listing, including the informed consent date, will be provided by subject ID number in ascending order.

### 5.2. Other Baseline Characteristics

Other baseline characteristics include body weight (in kg), height (in cm), body mass index (BMI; in kg/m^2). These baseline characteristics will be summarized by dose cohort within each treatment group and overall using descriptive statistics. The summary of baseline characteristics will be provided for the Safety Analysis Set.

A by-subject listing of these baseline characteristics will be provided by subject ID number in ascending order.

### 5.3. Medical History

Medical history will be collected at screening for disease-specific and general conditions (ie, conditions not specific to the disease being studied).

General medical history data will not be coded.

A by-subject listing of disease-specific and general medical history will be provided by subject ID number in ascending order.

### 5.4. Prior Anticancer Therapy

For prior anticancer therapies that a subject received before the start of the study drug, the number of prior regimens and the time since the completion of last regimen (ie, the most recent regimen that a subject received prior to the first dose date of the study drug) will be summarized by dose cohort within each treatment group and overall using descriptive statistics based on the the Safety Analysis Set.

For the completion of last regimen, a partial completion date will be imputed as follows:

- If day and month are missing but year is available, then the imputed day and month will be 01 Jan.

- If day is missing but the month and year are available, then the imputed day will be the first day of the month.
- Partial date will not be imputed if the year is missing.

A by-subject listing will be provided for prior anticancer therapies, on and post study anticancer therapies, prior and on-study radiation therapy, and prior and on-study surgery or procedures each by subject ID number in ascending order.

## 6. EFFICACY ANALYSES

### 6.1. Definitions of Efficacy Endpoints

#### 6.1.1. Progression-free survival (PFS)

Progression-free survival (PFS), defined as the interval from first dosing date of study drug to the earlier of the first documentation of definitive disease progression or death from any cause. Definitive disease progression is determined based on RECIST Version 1.1 {[Eisenhauer 2009](#)}.

The date of definitive progression will be the time point at which progression is first identified by relevant radiographic, imaging, or clinical data. Data will be censored on the date of last adequate tumor assessment (i.e. not “Not Evaluable” [NE]) for subjects:

- who do not have documented progression or die, or
- who start new anticancer therapy before documented progression, or
- who start new anticancer therapy before death without documented progression, or
- who have  $\geq 2$  consecutive missing tumor assessments immediate before documented progression, or
- who have  $\geq 2$  consecutive missing tumor assessments immediate before death without documented progression

Subjects without any post-baseline tumor assessment will be censored at Study Day 1. If a subject does not have a baseline tumor assessment, then PFS will be censored at Study Day 1, regardless of whether or not definitive progression or death has been observed.

When the date of initiation of anticancer therapy other than the study treatment is incomplete or missing, the following algorithm will be followed:

- If the day is missing but the month and year are available, then the imputed day will be the last day of the month.
- If the day and month are missing but year is available, then the imputed day and month will be 01Jan or the last day of the month for the last non-NE tumor assessment if they have the same year, whichever is later.

Every attempt will be made to ensure that complete death dates are recorded. In those rare instances where complete death dates are not recorded, the following algorithm will be used:

- If the day is missing but the month and year are available, then the imputed day will be the midpoint of the month or the last assessment date + 1, whichever is later.

- If the day and month are missing but year is available, then the imputed day and month will be 01Jan or the last day of the latest month that the subject was known to be alive if they have the same year, whichever is later.

### **6.1.2. Overall Response Rate (ORR)**

For each subject, the overall response will be categorized as CR, PR, SD, noncomplete response or non progressive disease, progressive disease (PD) or NE at each visit of assessment.

ORR is defined as the proportion of subjects who achieve best overall response (BOR) of CR or PR during the study based on RECIST Version 1.1. Confirmation of CR or PR at the subsequent time point is required for best overall response of CR or PR. Subjects, who do not have sufficient baseline or on-study tumor status information to be adequately assessed for response status (ie, those with best overall response of NE ) or received anticancer therapy other than the study treatment prior to achieving CR or PR, will be considered as nonresponders. All subjects in the FAS will be included in the denominator in calculation of ORR.

### **6.1.3. Clinical Benefit Rate (CBR)**

CBR is defined as the proportion of subjects who achieve best overall response of CR, PR or SD that lasts for  $\geq 24$  weeks during the study based on RECIST Version 1.1. Duration of SD is calculated from the first dose date of study drug to the first date of disease progression. All subjects in the FAS will be included in the denominator in the calculation of CBR.

## **6.2. Analysis of the Efficacy Endpoints**

### **6.2.1. Progression-free Survival**

Progression-free survival based on investigators' assessments will be summarized using Kaplan-Meier (KM) methods by dose cohort within treatment group for the FAS. The KM curve for PFS will be provided. All the driven endpoints will be listed.

### **6.2.2. Overall Response Rate And Clinical Benefit Rate**

The number and percentage of subjects in each response category (eg, CR, PR, SD, SD that lasts for  $\geq 24$  weeks, PD, and NE) will be summarized by dose cohort within treatment group for the FAS. ORR and CBR based on investigators' assessments will be calculated along with their 95% confidence intervals (CIs) based on the Clopper-Pearson method and summarized by dose cohort within treatment group for the FAS.

A by-subject listing of the overall response assessment data will be provided.

## 7. SAFETY ANALYSES

### 7.1. Adverse Events and Deaths

All Adverse Events (AEs) will be listed. The focus of AE summarization will be on treatment-emergent adverse events (TEAEs). AEs that occur before the first dose of study drug or > 30 days after the subject has been discontinued from study drug will be included in data listings.

#### 7.1.1. Adverse Event Dictionary

Clinical and laboratory adverse events (AEs) will be coded using the current version of MedDRA. System organ class (SOC), high-level group term (HLGT), high-level term (HLT), preferred term (PT), and lower-level term (LLT) will be provided in the AE dataset.

#### 7.1.2. Adverse Event Severity

Adverse events are graded by the investigator as Grade 1, 2, 3, 4, or 5 according to CTCAE Version 4.03. The severity grade of events for which the investigator did not record severity will be categorized as “missing” for tabular summaries and data listings. The missing category will be listed last in summary presentation.

#### 7.1.3. Relationship of Adverse Events to Study Drug

Related AEs are those for which the investigator selected “Related” on the AE CRF to the question of “Related to Study Treatment.” Relatedness will always default to the investigator’s choice, not that of the medical monitor. Events for which the investigator did not record relationship to study drug will be considered related to study drug for summary purposes. However, by-subject data listings will show the relationship as missing.

#### 7.1.4. Serious Adverse Events

Serious adverse events (SAEs) will be identified and captured as SAEs if the AEs met the definitions of SAEs that were specified in the study protocol. SAEs captured and stored in the clinical database will be reconciled with the SAE database from the Gilead Pharmacovigilance and Epidemiology (PVE) Department before data finalization.

#### 7.1.5. Treatment-Emergent Adverse Events

##### 7.1.5.1. Definition of Treatment-Emergent Adverse Events

Treatment-emergent adverse events (TEAEs) are defined as 1 or both of the following:

- Any AEs with an onset date on or after the study drug start date and no later than 30 days after permanent discontinuation of study drug
- Any AEs leading to premature discontinuation of study drug.

### 7.1.5.2. Incomplete Dates

If the onset date of the AE is incomplete and the AE stop date is not prior to the first dosing date of study drug, then the month and year (or year alone if month is not recorded) of onset determine whether an AE is treatment emergent. The event is considered treatment emergent if both of the following 2 criteria are met:

- The AE onset is the same as or after the month and year (or year) of the first dosing date of study drug, and
- The AE onset date is the same as or before the month and year (or year) of the date corresponding to 30 days after the date of the last dose of study drug.

An AE with completely missing onset and stop dates, or with the onset date missing and a stop date later than the first dosing date of study drug, will be considered to be treatment emergent. In addition, an AE with the onset date missing and incomplete stop date with the same or later month and year (or year alone if month is not recorded) as the first dosing date of study drug will be considered treatment emergent.

In case when the AE onset date is incomplete and needs to be imputed, the following algorithm will be followed:

- If the day is missing but the month and year are available, then the imputed day will be the first day of the month or the first dosing date if they have the same month and year, whichever is later.
- If the day and month are missing but year is available, then the imputed day and month will be 01Jan or the first dosing date if they have the same year, whichever is later.

## 7.1.6. Summaries of Adverse Events and Deaths

Treatment-emergent AEs will be summarized by dose cohort within each treatment group and overall based on the Safety Analysis Set.

### 7.1.6.1. Summaries of AE Incidence by Severity

The number and percentage of subjects who experienced at least one TEAE will be provided and summarized by SOC, HLT and PT. For other AEs described below, summaries will be provided by SOC and PT:

- TEAEs
- TEAEs with Grade 3 or higher
- TEAEs related to GS-5829
- Treatment-emergent SAEs

- Treatment-emergent SAEs related to GS-5829
- TEAEs leading to premature discontinuation of GS-5829
- TEAEs leading to dose modification of GS-5829
- TEAEs leading to temporary interruption of GS-5829
- TEAEs leading to death

For TEAEs and TEAEs related to GS-5829, summaries will be provided by SOC, PT and severity.

A brief, high-level summary of AEs described above will be provided to show the number and percentage of subjects who experienced the above AEs as well as the following:

- TEAEs related to exemstane or fulvestrant
- TEAEs related to GS-5829 with Grade 3 or higher
- TEAEs related to exemstane or fulvestrant with Grade 3 or higher
- Treatment-emergent SAEs related to exemstane or fulvestrant

In addition to the above summary tables, TEAEs and treatment emergent SAEs will be summarized by PT only in descending order of total frequency.

Multiple events will be counted only once per subject in each summary. Adverse events will be summarized and listed first in alphabetic order of SOC and then by PT in descending order of total frequency within each SOC. For summaries by severity, the most severe severity will be used for those AEs that occurred more than once in a given subject during the study.

In addition, by-subject data listings will be provided for the following:

- All AEs
- All AEs of Grade 3 or higher
- SAEs
- Deaths
- AEs leading to death
- AEs leading to premature discontinuation of GS-5829

- AEs leading to dose reduction of GS-5829
- AE leading to dose interruption of GS-5829.

A flag will be included in the listings to indicate whether the event is treatment emergent.

#### 7.1.6.2. Summary of Deaths

Summary of deaths will not be provided given that there is no occurrence of death reported during this study.

### 7.1.7. Additional Analysis of Adverse Events

#### 7.1.7.1. Dose Limiting Toxicity

A by-subject listing of the DLT AEs will be provided following the standard AE listing format.

#### 7.1.7.2. Treatment-Emergent Adverse Events (TEAE) of Interest

TEAEs of interest are determined based on the customized medical search terms (MSTs) provided by PVE based on the Standardized MedDRA Queries (SMQs). Analyses for TEAEs of interest will be performed for the following:

- Decreased Platelets: (The list of selected PTs is provided in [Appendix 3](#).)
- Haemorrhage: (The list of selected PTs is provided in [Appendix 4](#).)
- Diarrhoea: (The list of selected PTs is provided in [Appendix 5](#).)

The number and percentage of subjects who experienced at least one TEAE of interest will be provided and summarized by adverse event of interest (AEI) category, preferred term and severity in a way similar to the summaries of TEAEs (Section [7.1.6](#)).

A by-subject listing of TEAEs of interest will be provided.

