#### Appendix 4. List of Medical Search Terms for Haemorrhage

MedDRA Preferred Terms	MedDRA Code
Haemorrhagic adrenal infarction	10079902
Eye haematoma	10079891
Spontaneous hyphaema	10080110
Anal fissure haemorrhage	10079765
Paranasal sinus haemorrhage	10080108
Peripheral artery aneurysm rupture	10079908
Aortic annulus rupture	10079586
Abdominal wall haematoma	10067383
Abdominal wall haemorrhage	10067788
Abnormal clotting factor	10049862
Abnormal withdrawal bleeding	10069195
Acquired dysfibrinogenaemia	10051122
Acquired haemophilia	10053745
Acquired haemophilia with anti FVIII, XI, or XIII	10056496
Acquired protein S deficiency	10068370
Acquired Von Willebrand's disease	10069495
Activated partial thromboplastin time abnormal	10000631
Activated partial thromboplastin time prolonged	10000636
Activated partial thromboplastin time ratio abnormal	10075284
Activated partial thromboplastin time ratio fluctuation	10075286
Activated partial thromboplastin time ratio increased	10075287
Acute haemorrhagic leukoencephalitis	10058994
Acute haemorrhagic ulcerative colitis	10075634
Administration site bruise	10075094
Administration site haematoma	10075100
Administration site haemorrhage	10075101
Adrenal haematoma	10059194
Adrenal haemorrhage	10001361
Anal haemorrhage	10049555
Anal ulcer haemorrhage	10063896

MedDRA Preferred Terms	MedDRA Code
Anastomotic haemorrhage	10056346
Anastomotic ulcer haemorrhage	10002244
Aneurysm ruptured	10048380
Angina bullosa haemorrhagica	10064223
Anorectal varices haemorrhage	10068925
Anti factor IX antibody positive	10058748
Anti factor V antibody positive	10058745
Anti factor VII antibody positive	10058746
Anti factor VIII antibody positive	10049013
Anti factor X activity abnormal	10077670
Anti factor X activity increased	10077671
Anti factor X antibody positive	10058747
Anti factor XI antibody positive	10058749
Anti factor XII antibody positive	10058750
Antithrombin III increased	10051115
Aortic aneurysm rupture	10002886
Aortic dissection rupture	10068119
Aortic intramural haematoma	10067975
Aortic perforation	10075729
Aortic rupture	10060874
Aponeurosis contusion	10075330
Application site bruise	10050114
Application site haematoma	10068317
Application site haemorrhage	10072694
Application site purpura	10050182
Arterial haemorrhage	10060964
Arterial intramural haematoma	10074971
Arterial ligation	10003165
Arterial perforation	10075732
Arterial rupture	10003173
Arteriovenous fistula site haematoma	10055150

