Coagulation disorder neonatal	10009732
Coagulation factor decreased	10009736
Coagulation factor deficiency	10067787
Coagulation factor IX level abnormal	10061770
Coagulation factor IX level decreased	10009746
Coagulation factor mutation	10065442
Coagulation factor V level abnormal	10061771
Coagulation factor V level decreased	10009754
Coagulation factor VII level abnormal	10061772
Coagulation factor VII level decreased	10009761
Coagulation factor VIII level abnormal	10061773
Coagulation factor VIII level decreased	10009768
Coagulation factor X level abnormal	10061774
Coagulation factor X level decreased	10009775
Coagulation factor XI level abnormal	10061775
Coagulation factor XI level decreased	10009779
Coagulation factor XII level abnormal	10061776
Coagulation factor XII level decreased	10009783
Coagulation factor XIII level abnormal	10061777
Coagulation factor XIII level decreased	10009787
Coagulation time abnormal	10009791
Coagulation time prolonged	10009799
Coagulopathy	10009802

MedDRA Preferred Terms	MedDRA Code
Coital bleeding	10065019
Colonic haematoma	10009996
Congenital coagulopathy	10063563
Congenital dysfibrinogenaemia	10051123
Conjunctival haemorrhage	10010719
Contusion	10050584
Corneal bleeding	10051558
Cullen's sign	10059029
Cystitis haemorrhagic	10011793
Deep dissecting haematoma	10074718
Diarrhoea haemorrhagic	10012741
Dilutional coagulopathy	10060906
Disseminated intravascular coagulation	10013442
Diverticulitis intestinal haemorrhagic	10013541
Diverticulum intestinal haemorrhagic	10013560
Duodenal ulcer haemorrhage	10013839
Duodenitis haemorrhagic	10013865
Dysfunctional uterine bleeding	10013908
Ear haemorrhage	10014009
Ecchymosis	10014080
Encephalitis haemorrhagic	10014589
Endometriosis	10014778
Enterocolitis haemorrhagic	10014896
Epidural haemorrhage	10073681
Epistaxis	10015090
Ethanol gelation test positive	10062650
Exsanguination	10015719
Extra-axial haemorrhage	10078254
Extradural haematoma	10015769
Extravasation blood	10015867
Eye contusion	10073354

MedDRA Preferred Terms	MedDRA Code
Eye haemorrhage	10015926
Eyelid bleeding	10053196
Eyelid contusion	10075018
Eyelid haematoma	10064976
Factor I deficiency	10016075
Factor II deficiency	10016076
Factor III deficiency	10052473
Factor IX deficiency	10016077
Factor V deficiency	10048930
Factor VII deficiency	10016079
Factor VIII deficiency	10016080
Factor X deficiency	10052474
Factor Xa activity abnormal	10078667
Factor Xa activity decreased	10078676
Factor XI deficiency	10016082

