Factor XII deficiency	10051806
Factor XIII deficiency	10016083
Femoral artery perforation	10075739
Femoral vein perforation	10075745
Fibrin abnormal	10016575
Fibrin D dimer decreased	10016579
Fibrin D dimer increased	10016581
Fibrin decreased	10016584
Fibrin degradation products	10016585
Fibrin degradation products increased	10016588
Fibrinolysis abnormal	10016604
Fibrinolysis increased	10016607
Foetal-maternal haemorrhage	10016871
Gardner-Diamond syndrome	10078888
Gastric haemorrhage	10017788
Gastric occult blood positive	10067855

MedDRA Preferred Terms	MedDRA Code
Gastric ulcer haemorrhage	10017826
Gastric ulcer haemorrhage, obstructive	10017829
Gastric varices haemorrhage	10057572
Gastritis alcoholic haemorrhagic	10017857
Gastritis haemorrhagic	10017866
Gastroduodenal haemorrhage	10053768
Gastroduodenitis haemorrhagic	10048712
Gastrointestinal angiectasia	10078142
Gastrointestinal haemorrhage	10017955
Gastrointestinal organ contusion	10078655
Gastrointestinal polyp haemorrhage	10074437
Gastrointestinal ulcer haemorrhage	10056743
Genital contusion	10073355
Genital haemorrhage	10061178
Gingival bleeding	10018276
Graft haemorrhage	10063577
Grey Turner's sign	10075426
Haemarthrosis	10018829
Haematemesis	10018830
Haematochezia	10018836
Haematocoele	10018833
Haematoma	10018852
Haematoma evacuation	10060733
Haematoma infection	10051564
Haematosalpinx	10050468
Haematospermia	10018866
Haematotympanum	10063013
Haematuria	10018867
Haematuria traumatic	10018871
Haemobilia	10058947
Haemophilia	10061992

MedDRA Preferred Terms	MedDRA Code
Haemophilia A with anti factor VIII	10056492
Haemophilia A without inhibitors	10056493
Haemophilia B with anti factor IX	10056494
Haemophilia B without inhibitors	10056495
Haemophilic arthropathy	10065057
Haemophilic pseudotumour	10073770
Haemoptysis	10018964
Haemorrhage	10055798
Haemorrhage coronary artery	10055803
Haemorrhage foetal	10061191
Haemorrhage in pregnancy	10018981
Haemorrhage intracranial	10018985
Haemorrhage neonatal	10061993
Haemorrhage subcutaneous	10018999
Haemorrhage subepidermal	10019001
Haemorrhage urinary tract	10055847
Haemorrhagic anaemia	10052293
Haemorrhagic arteriovenous malformation	10064595
Haemorrhagic ascites	10059766
Haemorrhagic breast cyst	10077443
Haemorrhagic cerebral infarction	10019005
Haemorrhagic cyst	10059189
Haemorrhagic diathesis	10062713
Haemorrhagic disease of newborn	10019008
Haemorrhagic disorder	10019009
Haemorrhagic erosive gastritis	10067786
Haemorrhagic hepatic cyst	10067796

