Haemorrhagic infarction	10019013
Haemorrhagic necrotic pancreatitis	10076058
Haemorrhagic ovarian cyst	10060781
Haemorrhagic pneumonia	10077933

MedDRA Preferred Terms	MedDRA Code
Haemorrhagic stroke	10019016
Haemorrhagic thyroid cyst	10072256
Haemorrhagic transformation stroke	10055677
Haemorrhagic tumour necrosis	10054096
Haemorrhagic urticaria	10059499
Haemorrhagic varicella syndrome	10078873
Haemorrhagic vasculitis	10071252
Haemorrhoidal haemorrhage	10054787
Haemostasis	10067439
Haemothorax	10019027
Henoch-Schonlein purpura	10019617
Hepatic haemangioma rupture	10054885
Hepatic haematoma	10019676
Hepatic haemorrhage	10019677
Hereditary haemorrhagic telangiectasia	10019883
Hermansky-Pudlak syndrome	10071775
Hyperfibrinolysis	10074737
Hyphaema	10020923
Hypocoagulable state	10020973
Hypofibrinogenaemia	10051125
Hypoprothrombinaemia	10021085
Hypothrombinaemia	10058517
Hypothromboplastinaemia	10058518
Iliac artery perforation	10075731
Iliac artery rupture	10072789
Iliac vein perforation	10075744
Immune thrombocytopenic purpura	10074667
Implant site bruising	10063850
Implant site haematoma	10063780
Implant site haemorrhage	10053995
Incision site haematoma	10059241

MedDRA Preferred Terms	MedDRA Code
Incision site haemorrhage	10051100
Increased tendency to bruise	10021688
Induced abortion haemorrhage	10052844
Inferior vena cava perforation	10075742
Infusion site bruising	10059203
Infusion site haematoma	10065463
Infusion site haemorrhage	10065464
Injection site bruising	10022052
Injection site haematoma	10022066
Injection site haemorrhage	10022067
Instillation site bruise	10073630
Instillation site haematoma	10073609
Instillation site haemorrhage	10073610
Internal haemorrhage	10075192
International normalised ratio abnormal	10022592
International normalised ratio increased	10022595
Intestinal haematoma	10069829
Intestinal haemorrhage	10059175
Intestinal varices haemorrhage	10078058
Intra-abdominal haematoma	10056457
Intra-abdominal haemorrhage	10061249
Intracerebral haematoma evacuation	10062025
Intracranial haematoma	10059491
Intracranial tumour haemorrhage	10022775
Intraocular haematoma	10071934
Intrapartum haemorrhage	10067703
Intraventricular haemorrhage	10022840
Intraventricular haemorrhage neonatal	10022841
Iris haemorrhage	10057418
Joint microhaemorrhage	10077666
Kidney contusion	10023413

MedDRA Preferred Terms	MedDRA Code
Lacrimal haemorrhage	10069930
Large intestinal haemorrhage	10052534
Large intestinal ulcer haemorrhage	10061262

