Pituitary haemorrhage	10049760
Placenta praevia haemorrhage	10035121
Plasminogen activator inhibitor	10059620
Plasminogen activator inhibitor decreased	10059619
Plasminogen decreased	10035493
Plasminogen increased	10035495
Platelet factor 4 decreased	10060220
Polymenorrhagia	10064050
Post abortion haemorrhage	10036246
Post procedural contusion	10073353
Post procedural haematoma	10063188
Post procedural haematuria	10066225
Post procedural haemorrhage	10051077

MedDRA Preferred Terms	MedDRA Code
Post transfusion purpura	10072265
Postmenopausal haemorrhage	10055870
Postpartum haemorrhage	10036417
Post-traumatic punctate intraepidermal haemorrhage	10071639
Procedural haemorrhage	10071229
Proctitis haemorrhagic	10036778
Prostatic haemorrhage	10036960
Protein C increased	10060230
Protein S abnormal	10051736
Protein S increased	10051735
Prothrombin level abnormal	10037048
Prothrombin level decreased	10037050
Prothrombin time abnormal	10037057
Prothrombin time prolonged	10037063
Prothrombin time ratio abnormal	10061918
Prothrombin time ratio increased	10037068
Pulmonary alveolar haemorrhage	10037313
Pulmonary contusion	10037370
Pulmonary haematoma	10054991
Pulmonary haemorrhage	10037394
Puncture site haemorrhage	10051101
Purpura	10037549
Purpura fulminans	10037556
Purpura neonatal	10037557
Purpura non-thrombocytopenic	10057739
Purpura senile	10037560
Putamen haemorrhage	10058940
Radiation associated haemorrhage	10072281
Rectal haemorrhage	10038063
Rectal ulcer haemorrhage	10038081
Renal artery perforation	10075737

MedDRA Preferred Terms	MedDRA Code
Renal cyst haemorrhage	10059846
Renal haematoma	10038459
Renal haemorrhage	10038460
Respiratory tract haemorrhage	10038727
Respiratory tract haemorrhage neonatal	10038728
Retinal aneurysm rupture	10079121
Retinal haemorrhage	10038867
Retinopathy haemorrhagic	10051447
Retroperitoneal haematoma	10058360
Retroperitoneal haemorrhage	10038980
Retroplacental haematoma	10054798
Ruptured cerebral aneurysm	10039330
Russell's viper venom time abnormal	10059759
Scleral haemorrhage	10050508
Scrotal haematocoele	10061517
Scrotal haematoma	10039749
Shock haemorrhagic	10049771
Skin haemorrhage	10064265
Skin neoplasm bleeding	10060712
Skin ulcer haemorrhage	10050377
Small intestinal haemorrhage	10052535
Small intestinal ulcer haemorrhage	10061550
Soft tissue haemorrhage	10051297
Spermatic cord haemorrhage	10065742
Spinal cord haematoma	10076051
Spinal cord haemorrhage	10048992
Spinal epidural haematoma	10050162

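### Reported coagulation-test and other non-bleeding adverse events count towards the SAP's Haemorrhage category, and no bleeding-only row is planned

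*SAP*

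**What the plan says.** SAP 7.1.7.2 names three categories of interest: decreased platelets, haemorrhage and diarrhoea. On where the definitions come from it says: "TEAEs of interest are determined based on the customized medical search terms (MSTs) provided by PVE", on the basis of standardised MedDRA queries. The bleeding category is defined by reference only: "Haemorrhage: (The list of selected PTs is provided in" Appendix 4.

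The planned table is described as follows: "subjects who experienced at least one TEAE of interest will be provided and summarized by adverse event of interest (AEI) category". The same sentence adds preferred term and severity as further breakdowns and asks for a layout like the general TEAE summaries in Section 7.1.6. A by-subject listing of these events is also planned.

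Appendix 4 is one undivided list. Among true bleeding terms it includes laboratory results such as "Activated partial thromboplastin time prolonged", "International normalised ratio increased" and "Protein C increased", inherited and acquired clotting disorders, and items such as "Endometriosis" and arterial ligation. Neither the section nor the appendix defines a bleeding-only subset.

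**The concern.** The category row is the figure most readers will take away, and its label promises bleeding. As defined, it mixes two things: subjects who bled, and subjects with a reported coagulation abnormality or another listed non-bleeding term.

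The distinction matters for this drug because bleeding is a named safety question:

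- Protocol 3.2 makes bleeding of Grade 2 or higher a DLT.
- Protocol 1.2.3.1 reports an adrenal haemorrhage as a DLT in an earlier study.
- Protocol 5.4 bars anticoagulants because of unexplained bleeding in dogs.
- Protocol 1.2.2.2 notes that prothrombin and partial thromboplastin times were normal in the dogs that bled.

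The sponsor's own non-clinical data therefore show bleeding without abnormal clotting tests. A rate that pools the two describes neither cleanly.

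**Working it through.** The plan states no figure to reproduce. The check is a count of terms, a trace of how an event reaches the table, and the weight of one subject.

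**1. Terms in Appendix 4 that are not bleeding events (unique terms)**

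- Laboratory or investigation results (aPTT, INR, prothrombin time, fibrinogen, factor levels, anti-factor antibodies and similar): 83.
- Coagulation or clotting-factor disorders (factor deficiencies, haemophilias, coagulopathy and similar): 39.
- Sum: 83 + 39 = 122.
- Stricter split, leaving out three capillary fragility or permeability terms, haemorrhagic diathesis and haemorrhagic disorder: 122 − 3 − 2 = 117.
- Other terms that are not bleeding events (endometriosis, arterial ligation, gastrointestinal angiectasia, increased tendency to bruise and similar): about 10, giving about 122 + 10 = 132.

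The class boundaries are a matter of judgement, hence the range of 117 to 122. The term count does not measure how often such events occur. The protocol schedules only PT/INR and aPTT as coagulation tests. The terms that name those tests number 5 (aPTT) + 2 (INR) + 4 (prothrombin time) = 11.

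**2. How a laboratory finding reaches the table**

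- The table counts reported treatment-emergent adverse events, not laboratory values.
- Under Protocol 7.1.3, a laboratory abnormality without clinical significance is not an adverse event. One that needs intervention, or leads to interruption, modification or stopping of study drug, must be recorded as one.
- Protocol Appendix 2, footnote 14, places coagulation tests at Screening and before dosing on C1D1, C1D15 and C2D1. Only the last two follow the first GS-5829 dose. The table itself also marks an end-of-treatment draw.

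The route is narrow but open.

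**3. Two hypothetical subjects under the SAP rules**

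- Subject A has one qualifying event, a reported prolonged aPTT, and no bleed. The term is in Appendix 4, so A adds one to Haemorrhage.
- Subject B has Grade 1 epistaxis and a reported Grade 3 INR increase. SAP 7.1.6.1 keeps the most severe grade in summaries by severity. If the category row follows that rule, as the reference to Section 7.1.6 suggests, B appears as Grade 3 Haemorrhage although the bleed was Grade 1.

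**4. Weight of one subject like A**

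Shift in the category percentage = 100/n.

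| n | Where n comes from | Shift (points) |
|---|---|---|
| 3 | Escalation cohort, Protocol 3.2 | 100/3 = 33.3 |
| 6 | Minimum at the dose taken to Phase 2, Protocol 3.2 | 100/6 = 16.7 |
| 12 | Maximum at a dose level, Protocol Appendix 10 | 100/12 = 8.3 |
| 30 | Phase 1b maximum, Protocol 8.9 | 100/30 = 3.3 |

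**5. Can the bleeding-only rate be rebuilt?**

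Not from the preferred-term rows alone: two bleeding terms with one subject each may be one subject or two. The by-subject listing settles which, so the rate can be counted by hand.

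**The case against.** The case for leaving the list alone has real substance.

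- **A broad list is a legitimate screen.** The SAP says openly that the list is customised from standard queries, prints every term, and shows preferred terms beneath the category. Nothing is hidden. This stands, but a screen still needs a label that matches its content.
- **No decision depends on the figure.** DLT bleeding is defined separately in Protocol 3.2 and listed separately under SAP 7.1.7.1. The dose model uses DLT counts only. SAP 3 rules out formal testing, and SAP 1 says that the study stopped during escalation. This stands and sets the priority.
- **Coagulation events may be rare.** Entry requires an INR of 1.2 or less, anticoagulants are barred, and few scheduled draws follow the first dose. Many listed terms are congenital conditions or assays that the protocol does not schedule. This stands: neither the term count nor the shift of 8 to 33 points is an estimate of bias.

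Two stronger readings are tempting, and the documents do not support them. A reader might infer that any prolonged aPTT or raised D-dimer is reported as haemorrhage. It is not: the investigator must first record it as an adverse event, and D-dimer is not among the analytes in Protocol Table 6-1. A reader might also infer that the true bleeding rate is lost. It is not: the listing preserves it, and what is missing is a displayed subtotal.

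**Conclusion.** The point holds as a minor matter of definition and presentation. As written, the Haemorrhage row can include subjects who did not bleed, and its worst grade can come from a laboratory event. The list contains 117 to 122 laboratory and coagulation terms, plus about ten others that are not bleeding events.

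The shift of 33.3 points at n = 3, falling to 8.3 at n = 12, assumes one subject with a non-bleeding qualifying event and no bleeding event. Whether there is one cannot be told from the documents. The statement about severity assumes that the category row follows the worst-grade rule of SAP 7.1.6.1. No primary result, test or dose decision is affected.

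**What to change.** Flag each Appendix 4 term as either (a) a clinical bleeding event or (b) a coagulation laboratory, factor, antibody or other non-bleeding term. Report (a) as Haemorrhage and (b) as a separate row with its own label, each by preferred term and severity. State that the worst grade in each row comes from that row's own terms. Carry the flag into the by-subject listing.

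No information is lost, because both sets are still reported. Coagulation results also remain visible in the laboratory listings and summaries of SAP 7.2. The cost is one flag in a list that is already customised and one extra table row. SAP 1 has the plan finalised before data finalisation and lets later changes be documented in the CSR, so either route is open.
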